Based on the nonclinical data on M8891 showing evidence of tumor stasis and prolonged survival after single-agent use in xenograft models, and after combination with cabozantinib in RCC patient-derived xenograft models, the conduct of this trial is considered justifiable using the dose(s) and dosage regimen(s) of the investigational drug as specified in this clinical trial protocol. Refer to the M8891 Investigator's Brochure (IB) for further information about the nonclinical program. Based on the clinical data to date from the ongoing single agent study with M8891 (Part 1) and the known safety profile of cabozantinib, the safety measures such as stringent eligibility, routine safety monitoring along with AE reporting for the proposed study are considered adequate.

This clinical trial will be conducted in compliance with the clinical trial protocol, ICH GCP and any additional applicable regulatory requirements.

3.3.1

[figure not shown]
M8891

More detailed information about the anticipated benefits and risks based on nonclinical data of M8891 is presented in Section 3.1 and the M8891 IB.

CCI

CCI

Based on the currently available data, M8891 (parent drug) is predicted to exhibit a low drug-drug interaction (DDI) potential as perpetrator of CYP3A4 sensitive substrates at doses at the upper range of the estimated BED (60 mg QD). The DDI potential as victim of strong CYP3A4, 2C19 and 2C9 inhibitors is predicted to be weak, and as victim of a combined CYP3A4, 2C19 and 2C9 inhibitor to be only in the moderate range.

CCI

No relevant effects on cardiovascular, respiratory, or central nervous system function are anticipated from the in vitro and in vivo safety pharmacology studies for the expected clinically relevant exposures.

The lymphatic and hematopoietic system including the bone marrow, the spermatogenetic epithelium and epithelia of the gastrointestinal tract were the main toxicity target organs of M8891 in pivotal 4-week oral repeat-dose toxicity studies in rats and dogs with no observed adverse effect levels (NOAELs) of 3 mg/kg/day and 0.75 mg/kg/day, respectively. M8891 was devoid of genotoxic, phototoxic and skin irritating potential.

CCI

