Each part of the study will include a Screening period of up to 28 days, a study intervention period consisting of 21-day cycles of M8891 single agent (Part 1) and M8891 combined with cabozantinib (Part 2), an End of Study Intervention visit (within 7 days), and a Safety Follow-up period of 30 (\pm 7) days. Subjects who discontinue study intervention for any reason will complete the End of Study Intervention and Safety Follow-up visits. In Part 2A, before Cycle 1 of all dose levels, subjects will receive a single dose of M8891 in the morning in fed conditions (Day -1, Cycle 1) and the PK profile of M8891 will be evaluated pre-dose, 1, 2, 3, 4, 6, 8 and 24h (Day 1, Cycle 1) after administration (Section 5.1.3.2.1). Subsequently on Day 1 Cycle 1, subjects will initiate

treatment with M8891 combined with cabozantinib QD orally every morning under fasted conditions.

Study duration per subject is approximately 8 months for Part 1, and 12 months for Part 2 including screening, treatment and follow up.

[figure not shown]
The design of this study is presented in

Figure 1 and a detailed Schedule of Assessments (SoAs) is provided in Table 1, Table 2, Table 3, Table 4, and Table 5.

Figure 1

Study Design

AE: Adverse event; DL: Dose level; FBE Free-base equivalent; MTD: Maximum tolerated dose; QD: Once daily; SMC: Safety Monitoring Committee; RP2D: Recommended Phase 2 Dose; mRCC: metastatic renal cell carcinoma; **CCI** [REDACTED].

- a. The MTD of M8891 single agent will be defined, and RP2D of M8891 single agent suggested, by the SMC.
- b. Subjects should have progressed to 1 or more previous lines of systemic anticancer therapy, excluding treatment with cabozantinib.
- c. Cabozantinib will be given at the approved 60 mg FBE daily dosage with dosage adjustments to 40 mg or 20 mg permitted to manage AEs.

CCI [REDACTED]

CCI [REDACTED]

- f. 30 subjects evaluable for response.
- g. The DLT assessment period for Part 2A is the Cycle 1 (= 22 days, 21 days of M8891 combined with cabozantinib, preceded by 1 day of M8891 alone) of study treatment. The rest of the Cycles in Part 2A are 21-day cycles of M8891 combined with cabozantinib.
- h. See Section 8.5.1 for the Bayesian two-parameter logistic regression model.

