For Part 1, all subjects will complete an End of Treatment (EOT) Visit 30 (\pm 3) days after the last dose of study drug. For Part 2, all subjects will complete an EOT visit within 7 days after the last dose of study drug. For both Part 1 and Part 2, subjects with serious AEs (SAEs) ongoing at EOT Visit must be followed during the safety follow-up by the Investigator until stabilization or until the outcome is known, unless the subject is documented as “lost to follow-up”.

Subjects who tolerate M8891 (or M8891 combined with cabozantinib) without significant clinically relevant toxicities may continue to receive trial treatment, at the Investigator’s discretion or after consultation with the Sponsor’s physician, as long as there is no evidence of disease progression.

5.2

Discussion of Trial Design

This is a 2-part, Phase I/Ib, first in human, multicenter, open-label trial of M8891 single agent in solid tumors and M8891 combined with cabozantinib in mRCC, administered daily.

5.2.1

Dose Selection

5.2.1.1

Part 1, M8891 Single Agent, Solid Tumors

ICH guideline S9 has been considered as the reference guideline for the determination of the first-in-human starting dose, i.e., a dose that is expected to have pharmacologic effects and reasonably safe to use.

Based on the toxicity profile of M8891 administered to rats and dogs in the 2 pivotal 4-week repeat-dose oral toxicity studies, defining NOAELs of 3 mg/kg in rats and 0.75 mg/kg in dogs, the dog was identified to be the most sensitive species (Table 11). The NOAEL of 0.75 mg/kg dose in dogs also corresponded to the highest non-severely toxic dose (HNSTD). According to ICH guideline S9, when the non-rodent is the most appropriate species, 1/6 of the HNSTD is considered an appropriate starting dose. Hence, the proposed first-in-human starting dose for Part 1 of the

study was calculated to be 7.5 mg (rounded to 7 mg)/subject/day. In the first cohorts of subjects with late stage advanced malignancies, this dose will be given as a once daily oral administration.

Table 11 **First in Human Starting Dose Calculated from Results of 4-week Repeat-Dose Toxicity Studies in Rats and Dogs**

Species	Treatment regimen	NOAEL (mg/kg/day)	Safety factor	Starting dose based on NOAEL (mg per subject) ^a
Rat	Daily, oral	3	1/10	18
Dog	Daily, oral	0.75 ^b	1/6	7.5

NOAEL: No observed adverse effect level.

^a Based on the assumption of 60 kg patient.

^b Corresponds to the highest non-severely toxic dose.

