5.3.1 Inclusion Criteria

5.3.1.1 Part 1, M8891 Single Agent, Solid Tumors

Subjects are eligible to be included in the study only if all the following criteria apply:

1. Subjects must be refractory to or intolerant of existing cancer therapy(ies) known to provide clinical benefit.
2. Histologically confirmed advanced solid tumors with no clear curative treatment options available after at least 1 prior systemic anticancer therapy
3. Male and female subjects age 18 years and older who are able and willing to give written informed consent
4. A male subject must agree to use and to have their female partners to use a highly effective contraception (i.e., methods with a failure rate of less than 1% per year) as detailed in [Appendix I](#) of this protocol before first dose of study treatment (as appropriate), during the treatment period and for at least 92 days (3 months) after the last dose of study treatment and refrain from donating sperm during this period.
5. A female subject is eligible to participate if she is not pregnant (see [Appendix I](#)), not breastfeeding, and at least one of the following conditions applies:
 - a. Not a woman of childbearing potential (WOCBP) as defined in [Appendix I](#)
 - b. A WOCBP who agrees to use a highly effective contraception (i.e., methods with a failure rate of less than 1% per year) as detailed in [Appendix I](#) of this protocol before start of first dose of study treatment (as appropriate), during the treatment period and for at least 92 days (3 months) after the last dose of study treatment.
6. Tumor accessible for biopsies and agreement to conduct pre-dose and post-dose fresh tumor biopsies. Archival tumor tissue is not mandatory for the inclusion in the study but is strongly recommended.

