12. A male subject must agree to use and to have their female partners use a highly effective contraception (i.e., methods with a failure rate of less than 1% per year) as detailed in [Appendix I](#) of this protocol before first dose of study treatment (as appropriate), during the treatment

period and for at least 92 days (3 months) after the last dose of study treatment and refrain from donating sperm during this period.

13. A female subject is eligible to participate if she is not pregnant (see [Appendix I](#)), not breastfeeding, and at least one of the following conditions applies:

a. Not a woman of childbearing potential (WOCBP) as defined in [Appendix I](#)

OR

b. A WOCBP:

- who agrees to use a highly effective contraception (i.e., methods with a failure rate of less than 1% per year) as detailed in Appendix I of this protocol before start of first dose of study treatment (as appropriate), during the treatment period and for at least 92 days (3 months) after the last dose of study treatment.
- Who has a negative serum pregnancy test at the Screening Visit and a negative urine pregnancy test on Day 1 before dosing, as required by local regulations, within 24 hours before the first dose of study intervention.

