7.4.1.3 Definition of the Adverse Event Reporting Period

The AE reporting period for safety surveillance begins when the subject is initially included in the trial (date of first signature of first informed consent) and continues until the EOT visit and through the safety follow-up period for SAEs. Subjects with SAEs ongoing at EOT Visit must be followed during the safety follow-up.

Any SAE assessed as related to M8891 must be reported whenever it occurs, irrespective of the time elapsed since the last administration of M8891.

7.4.1.4 Procedure for Reporting Serious Adverse Events, Adverse Events of Special Interest and Dose Limiting Toxicities

Serious Adverse Events

In the event of any new SAE occurring during the reporting period, the Investigator must immediately (within a maximum of 24 HOURS after becoming aware of the event) inform the Sponsor or its designee in writing. All written reports should be transmitted using the SAE Report Form, which must be completed by the Investigator following specific completion instructions.

In exceptional circumstances, an SAE (or follow-up information) may be reported by telephone; in these cases, a written report must be sent immediately thereafter by fax or e-mail. Names, addresses, and telephone and fax numbers for SAE reporting will be included in the trial-specific SAE Report Form.

Relevant pages from the eCRF may be provided in parallel (for example, medical history, concomitant drugs). Additional documents may be provided by the Investigator, if available (for example, laboratory results, hospital report, autopsy report). In all cases, the information provided on the SAE Report Form must be consistent with the data about the event recorded in the eCRF.

The Investigator must respond to any request for follow-up information (for example, additional information, outcome, final evaluation, other records where needed) or to any question the Sponsor/designee may have on the AE within the same timelines as those noted above for initial reports. This is necessary to ensure prompt assessment of the event by the Sponsor or designee and (as applicable) to allow the Sponsor to meet strict regulatory timelines associated with expedited safety reporting obligations.

Requests for follow-up will usually be made via the responsible Monitor, although in exceptional circumstances the Global Drug Safety department may contact the Investigator directly to obtain further information or to discuss the event.

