AEs are recorded and assessed continuously throughout the trial (see Section 7.4.1.3) and are assessed for final outcome at the EOT Visit. All SAEs ongoing at EOT Visit must be followed during the safety follow-up period. The safety follow-up must be monitored and followed up by the Investigator until stabilization or until the outcome is known, unless the subject is documented as “lost to follow-up”. Reasonable attempts to obtain this information must be made and documented. It is also the responsibility of the Investigator to ensure that any necessary additional therapeutic measures and follow-up procedures are performed.

7.4.2

Pregnancy and In Utero Drug Exposure

Only pregnancies considered by the Investigator to be related to trial treatment (for example, resulting from a drug interaction with a contraceptive medication) are considered to be AEs. However, all pregnancies with an estimated conception date during the period defined in Section 7.4.1.3 must be recorded by convention in the AE page/section of the eCRF. The same rule applies to pregnancies in female subjects and to pregnancies in female partners of male subjects. The Investigator must notify the Sponsor/designee in an expedited manner of any pregnancy using the Pregnancy Report Form, which must be transmitted according to the same process as described for SAE reporting in Section 7.4.1.4.

Investigators must actively follow up, document and report on the outcome of all these pregnancies, even if the subjects are withdrawn from the trial.

The Investigator must notify the Sponsor/designee of these outcomes using the Pregnancy Report Form. If an abnormal outcome occurs, the SAE Report Form will be used if the subject sustains an event and the Parent-Child/Fetus Adverse Event Report Form if the child/fetus sustains an event.

Any abnormal outcome must be reported in an expedited manner as described in Section 7.4.1.4, while normal outcomes must be reported within 45 days after delivery.

In the event of a pregnancy in a subject occurring during the course of the trial, the subject must be discontinued from trial medication immediately. The Sponsor/designee must be notified without delay and the subject must be followed as mentioned above.

7.4.3

Clinical Laboratory Assessments

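### Pregnancy recording ends at EOT or about Day 30, but contraception is required to Day 92, leaving 55 to 85 post-dose days with no stated recording requirement

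*Protocol*

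**What the plan says.** **Contraception.** Inclusion criteria 4 and 5 (Part 1) and 12 and 13 (Part 2) require highly effective contraception "during the treatment period and for at least 92 days (3 months) after the last dose of study treatment". For men the text runs "for at least 92 days (3 months) after the last dose of study treatment and refrain from donating sperm during this period". Appendix I repeats the 92 days. Deviations 213 and 214 in SAP Appendix 18.1 use the same 92-day horizon and class a failure of the contraception requirement as an important protocol deviation.

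**Recording.** Section 7.4.2 states that "all pregnancies with an estimated conception date during the period defined in Section 7.4.1.3 must be recorded", and applies this to female subjects and to partners of male subjects. The period in Section 7.4.1.3 starts at consent and "continues until the EOT visit and through the safety follow-up period for SAEs".

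**When the period ends.** Section 5.1.4 says: "For Part 1, all subjects will complete an End of Treatment (EOT) Visit 30" (± 3) days after the last dose. It then says: "For Part 2, all subjects will complete an EOT visit within 7 days after the last dose of study drug". Tables 2 and 3 show a +7 visit window on the Part 2 EOT column. Section 5.1 adds an end-of-intervention visit "and a Safety Follow-up period of 30" (± 7) days; Tables 2 and 3 place the Part 2 safety follow-up 30 days after the last dose.

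**Other duties in Section 7.4.2.** The investigator must notify the sponsor of any pregnancy on the Pregnancy Report Form, by the SAE route, and must follow these pregnancies to outcome. Neither sentence gives a date limit of its own.

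**The concern.** The 92 days are the sponsor's own statement of how long after dosing a conception should be avoided. The recording rule uses a different and much shorter clock. A female subject, or a male subject's partner, who conceives on Day 40 after the last dose falls inside the contraception window but outside any recording window that the text defines.

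This is a first-in-human MetAP2 inhibitor. Section 3.3.1 reports that, with the lymphatic and hematopoietic system, "the spermatogenetic epithelium and epithelia of the gastrointestinal tract were the main toxicity target organs" in the animal studies. If sites apply the rule as written, pregnancies after a late contraceptive failure need not enter the study record. In-utero exposure information for the post-treatment period would then depend on spontaneous reports.

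**Working it through.** No sample-size, power or error-rate figure bears on this point. The check is a comparison of windows.

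**Inputs.** Contraception window W = 92 days after the last dose (inclusion criteria, Appendix I). Let d be the last post-dose day on which a conception falls within the Section 7.4.1.3 period. Section 7.4.2 does not say whether pregnancies follow the general adverse event limit (EOT) or the SAE limit (safety follow-up), so both are taken for Part 2.

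**Formulas.** Days without a recording requirement = W − d. Share = (W − d)/W.

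| Reading | d | 92 − d | Share |
|---|---|---|---|
| Part 2, EOT at Day 7 | 7 | 85 | 92.4% |
| Part 2, EOT with +7 window | 14 | 78 | 84.8% |
| Part 2, safety follow-up, early | 23 | 69 | 75.0% |
| Part 2, safety follow-up, nominal | 30 | 62 | 67.4% |
| Part 2, safety follow-up, late | 37 | 55 | 59.8% |
| Part 1, EOT early | 27 | 65 | 70.7% |
| Part 1, EOT nominal | 30 | 62 | 67.4% |
| Part 1, EOT late | 33 | 59 | 64.1% |

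The gap exceeds half of the 92 days whenever d is below 92/2 = 46. Every row meets that. The 85-day figure takes EOT on the last day that Section 5.1.4 allows; an earlier visit leaves more days uncovered.

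**Part 1.** Safety follow-up is not credited here. It comes after an EOT already near Day 30, Table 1 gives it no day, and it is done only if an SAE is unresolved at EOT. Stacking 30 further days on a Day 30 EOT would give d = 60 and still leave 92 − 60 = 32 days.

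**Share of the whole contraception period.** Contraception also covers treatment, when recording applies in full. Assume treatment equals the stated study duration less 28 days of screening and 30 days of follow-up, at 30.4375 days per month (SAP Section 9).
- Part 1: 8 × 30.4375 − 58 = 185.5 days, so 62/(185.5 + 92) = 22.3%.
- Part 2: 12 × 30.4375 − 58 = 307.25 days, so 85/(307.25 + 92) = 21.3% on the EOT reading and 62/399.25 = 15.5% at Day 30.
- Shorter treatment raises the share. On the Part 2 EOT reading it passes 50% only if treatment lasts less than 2 × 85 − 92 = 78 days.

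**The case against.** Three stronger claims are tempting, and the documents do not carry them.

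**That a pregnancy counts only if conceived by EOT.** This is one of two readings. Section 7.4.1.3 extends to safety follow-up for SAEs, and Section 7.4.2 sends pregnancies by the SAE route. Tables 2 and 3 mark adverse event assessment at the Day 30 visit, and Appendix III lists a urine pregnancy test at follow-up. Section 5.1 has every discontinuing subject complete safety follow-up, although the footnotes to Tables 2 and 3 limit it to subjects with an unresolved SAE. Day 30 is therefore a fair alternative to Day 7 in Part 2. This stands, and it is why the result is a range.

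**That later conceptions are neither reported nor followed.** The conception-date limit attaches to recording in the case report form. The notification sentence covers any pregnancy without a date, and the outcome sentence can be read as referring to it. SAEs judged related to M8891 are reportable without time limit. So the text does not exclude late reports. It does not require them clearly either: the SAE procedure in Section 7.4.1.4 concerns events in the reporting period, an uncomplicated pregnancy is not an SAE, and a Day 30 urine test can show neither a partner's pregnancy nor a later conception.

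**That most of the contraception period is unobserved.** This holds for the 92 post-dose days only. Over treatment plus 92 days the share is roughly 16% to 22% under the assumption shown.

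Section 3.3.1 also reports no genotoxic potential, which tempers the concern about male exposure. Parts of that section are redacted and the consent pages are not available, so what subjects are told about late pregnancies cannot be judged.

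**Conclusion.** The two windows do not match. Recording is required for conceptions up to EOT or, on the more generous Part 2 reading, up to safety follow-up, while contraception is required to at least Day 92. Between 55 and 85 of the 92 post-dose days (60% to 92%) have no stated recording requirement, and no passage sets a pregnancy window or contact out to Day 92. Whether later conceptions must be notified and followed to outcome is unclear.

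The range assumes that Part 1 ends at EOT as set in Section 5.1.4, and that the Part 2 safety follow-up is counted from the last dose as in Tables 2 and 3. The point concerns safety capture. It changes no endpoint, analysis set, sample size or dose decision.

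**What to change.** In Section 7.4.2, replace the reference to the Section 7.4.1.3 period with an explicit window: from informed consent through 92 days after the last dose of study treatment, for female subjects and for partners of male subjects. State that notification on the Pregnancy Report Form and follow-up to outcome cover the same window. At EOT, instruct subjects to tell the site of any conception up to that day.

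This uses the protocol's existing 92 days and leaves the contraception rules untouched. It adds no visit and no test. The cost is a short text change, one instruction at EOT, and an occasional Pregnancy Report Form after a subject has left the trial. The statements on who attends safety follow-up (Section 5.1 against the footnotes to Tables 2 and 3) should be reconciled in the same amendment.

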7.4.4 Vital Signs, Physical Examinations, and Other Assessments

Vital sign, physical exam, and other assessments include: heart rate, diastolic blood pressure systolic blood pressure, weight, temperature, and additional assessments as included in Table 1, Table 2, and Table 3.

For timings of assessments, see the SoAs (Table 1, Table 2, and Table 3). For detailed procedures refer to the Manual of Operations.

7.4.5 Electrocardiograms

ECG will be performed throughout the study at specified time points (during Part 1 and Part 2) as indicated in the SoAs (Table 1 for Part 1, and Table 4 and Table 5 for Part 2).

The Fridericia formula is depicted below for calculation of the corrected QT (QTcF) interval.

$QTcF \text{ interval} = QT/RR^{1/3}$, where QT = measured QT interval in milliseconds; RR = measured R to R interval (which can be derived from the heart rate as 60/heart rate).

7.4.5.1 Part 1 M8891 Single Agent, Solid Tumors

ECGs for QT/QTc Evaluation

At screening, standard triplicate (within 2 min) digital 12-lead ECG will be obtained after the subject has been rested in semi-recumbent position for at least 5 min using standard 12-lead equipment to determine the QTcF interval. If the average of these three consecutive results for QTcF interval is > 480 ms the subject does not meet eligibility in this regard.

12-lead triplicate digital ECG will be performed within 2-minutes after at least 10 minutes rest in supine position, on Cycle 1 Day 1 and Day 15 at pre-dose and 1, 2, 4, 5, 6, 8, 12 hours and 24 hours post-dose (\pm 15 minutes) and on pre-dose on Day 8. The SMC may decide that the Day 15/Day 16 assessment can be waived in case no relevant drug accumulation is being observed. ECG assessments at subsequent cycles will be performed pre-dose at time points as indicated in Table 1. ECGs should be performed directly before PK sampling time-points on days where both assessments are performed.

Digital ECGs will be stored for a later independent analysis: ECG extractions will be made by the central ECG laboratory and over-read of interval measurements will be provided by experienced, qualified, and certified cardiac safety specialists. The readers will be blinded to subject details, treatment, visit day, and time points of the ECG recording, and a single reader will read all ECGs of a given subject. Time-matched, replicate ECGs and PK samples collected will be used to analyze for QTcF interval responses using slope analysis of exposure/response. This analysis may be reported separately.

7.4.5.2

Part 2 M8891 with cabozantinib, mRCC

Safety ECGs

Safety ECGs are standard triplicate 12-lead ECGs obtained for safety monitoring according to the SoAs (Table 4 for Part 2A and Table 5 for Part 2B). Subjects will rest in semi-recumbent position for at least 5 minutes. Safety ECGs will be read locally, and all ECGs should be assessed on the day of collection to determine continued eligibility. The calculated QTcF interval average of 3 12-lead ECGs must be \leq 450 ms for males and \leq 470 ms for female participants' eligibility. To confirm suitability for treatment after screening, ECGs must be repeated on Day -1, Cycle 1, prior to administering the first dose of study treatment unless the screening tests were performed within 14 days prior to first dose.

During the scheduled safety visits, subjects, in whom the calculated QTcF interval average increases to $>$ 500 ms or $>$ 60 ms change over baseline during treatment with M8891 combined with cabozantinib, must interrupt study treatment until further clinical evaluation. ECGs should be repeated if QTcF interval is outside the range until resolution (Table 12, Section 6.5.5). To assess the safety and tolerability of the study intervention, an ECG can be repeated at the Investigator's discretion at unscheduled visits. Start and end of resting time and ECG time will be recorded in the eCRF.

Abnormalities in the ECG that lead to a change in subject management (e.g., dose reduced or withheld, treatment discontinued, requirement for additional medication or monitoring as described in Table 12, Section 6.5.5) or result in clinical signs and symptoms are considered clinically significant for the purposes of this study and will be deemed adverse events. If values meet criteria defining them as serious, they must be reported as SAEs.

7.5

Pharmacokinetics

7.5.1

Part 1, M8891 Single Agent, Solid Tumors

For the PK analysis, the plasma level of M8891 will be analyzed by the analytical laboratory selected under responsibility of the Sponsor, using an appropriate validated bioanalytical method. Urine level of M8891 will be analyzed using an appropriate qualified method.

Full details of the bioanalytical method used will be described in a separate bioanalytical report. Plasma concentrations of M8891 and its metabolites will be analyzed as indicated in Table 1.

At each time point, 3 mL (2 aliquots of 1.5 mL) blood will be collected. The exact blood volume will be indicated in the Laboratory Manual. For all clinical and research studies, the total blood volume (mL) drawn in a 30-day period will never exceed the 280 mL.

Actual date and time of M8891 administration and PK actual sampling date and time will be recorded in the eCRF.

The PK sampling (and corresponding CCI sampling) schedule may be modified based upon emerging PK information collected during the study with the provision that the overall amount of blood to be collected for PK sampling is not increased.

List of PK parameters:

- C_{max} : Observed maximum plasma concentration
- t_{max} : Time to reach maximum observed plasma concentration
- $AUC_{0-\infty}$: Area under the concentration-time curve from time zero extrapolated to infinity, based on the predicted value for the concentration at t_{last}
- AUC_{0-t} : Area under the concentration-time curve from time zero to the last sampling time at which the concentration is at or above the lower limit of quantification (LLOQ)
- $AUC_{0-\tau}$: Area under the plasma concentration versus time curve within one dosing interval
- $t_{1/2}$: Apparent terminal half-life
- λ_z : Apparent terminal rate constant
- CL/F : Apparent body clearance of drug following extravascular administration
- CL_{ss}/F : Apparent body clearance of drug following extravascular administration at steady state
- V_z/F : Apparent volume of distribution during the terminal phase following extravascular administration
- $Racc(AUC_\tau)$: Accumulation ratio for AUC_τ
- $Racc(C_{max})$: Accumulation ratio for C_{max} .

In dose level 4 and dose level 5, urine samples for exploratory determination of M8891 and its metabolites will be taken from the total pooled urine sample provided during the 12-hour collection period on Day 1 and Day 15. The start and stop date/time of each pooled urine collection should be recorded in the eCRF. The volume of each urine collection will also be recorded.

Additional analyses may be conducted on the plasma and/or urine samples to further investigate the presence and/or identity of drug metabolites. Any results from such analyses on plasma and/or urine may be reported separately from the clinical trial report.

Details on sample shipment and handling will be provided in the Laboratory Manual.

